7.1.2.1 Assessment of Expectedness

The expectedness of an AE shall be determined by the sponsor according to the Summary of Product Characteristics (SmPC) in Europe (Marketing authorisation number EU/1/17/1224/001 and EU/1/17/1224/002).

7.1.2.2 Follow-Up of Adverse Events

Any AEs already recorded and designated as "continuing" should be reviewed at each subsequent assessment.

If an AE is still present at the end of the study, reasonable follow-up clinical monitoring should be managed by the investigator or any appropriate physician until the event or its sequelae resolves or stabilises at an acceptable level, as judged by the investigator. The frequency of follow-up evaluation is left to the investigator's discretion.

7.1.2.3 Reporting of Adverse Events

Any AE considered related to study drug administration that the investigator becomes aware of after completion of the EoS/ED visit must be reported to the sponsor and will be recorded in the corresponding database, adverse events in the clinical database, serious adverse events in the safety database.

7.1.3 Serious Adverse Event Assessment and Reporting to Sponsor

The investigator must pursue and obtain information adequate both to determine the outcome of the AE and to assess whether it meets criteria for classification as a Serious AE (SAE) requiring immediate notification to the global patient safety department of the sponsor.

An SAE is any AE that:

- Results in death,
- Is life-threatening, that is any event that places the subject at immediate risk of death from the event as it occurs. It does not include an event that, had it occurred in a more severe form, might have caused death,
- Results in in-patient hospitalisation or prolongation of existing hospitalisation, excluding admission for social or administrative reasons,

- Hospitalisation is defined as any in-patient admission (even if less than 24 hours). For chronic or long term in-patients, in-patient admission also includes transfer within the hospital to an acute/intensive care in-patient unit,
- Prolongation of hospitalisation is defined as any extension of an in-patient hospitalisation beyond the stay anticipated/required in relation to the original reason for the initial admission, as determined by the investigator or treating physician. For protocol-specified hospitalisation in clinical studies, prolongation is defined as any extension beyond the length of stay described in the protocol. Prolongation in the absence of a precipitating, treatment emergent, clinical AE (i.e. not associated with the development of a new AE or worsening of a pre-existing condition) may meet criteria for “seriousness” but is not an adverse experience and thus is not subject to immediate reporting to the sponsor,
- Preplanned or elective treatments/surgical procedures should be noted in the subject's screening documentation. Hospitalisation for a preplanned or elective treatment/surgical procedure should not be reported as an SAE unless there are complications or sequelae which meet the criteria for seriousness described above,
- Results in a persistent or significant disability/incapacity, where disability is a substantial disruption of a person's ability to conduct normal life functions,
- Results in congenital anomaly/birth defect in the offspring of a subject who received the study drug,
- Is an important medical event that may not result in death, be life-threatening, or require hospitalisation when, based upon appropriate medical judgement, may jeopardise the subject and may require medical or surgical intervention to prevent one of the outcomes listed in this definition. Examples of such medical events include allergic bronchospasm requiring intensive treatment in an emergency room or at home, blood dyscrasias, or convulsions that do not result in in-patient hospitalisation, or the development of drug dependency or drug abuse.

All SAEs, regardless of treatment group or suspected relationship to study drug, must be reported immediately (**within 24 hours** of the investigator's knowledge of the event) using the fax number or the e-mail address specified on the front page of the current document, up to 30 days after last administration.

Any appropriate means of notification may be used. If the immediate report is submitted by telephone, this must be followed by detailed written reports using the SAE report form.

The following information is the minimum that must be provided to the sponsor:

- Study number,
- CRU/Investigational site identification,
- Subject number,
- AE,
- Investigator's name and contact details.

The additional information included in the SAE form must be provided to the sponsor or representative as soon as it is available. The investigator should always provide an assessment of causality for each event reported to the sponsor. Upon receipt of the initial report, the sponsor will ask for the investigator's causality assessment if it was not provided with the initial report.

The investigator should report a diagnosis or a syndrome rather than individual signs or symptoms. The investigator should also try to separate a primary AE considered as the foremost untoward medical occurrence from secondary AEs which occurred as complications.

7.1.4 Suspected Unexpected Serious Adverse Reactions

Suspected unexpected serious adverse reactions (SUSARs) are serious events that are not listed in the approved SmPC in Europe (Marketing authorisation number EU/1/17/1224/001 and EU/1/17/1224/002) and that the investigator identifies as related to the study drug or study procedure.

7.1.5 Pregnancy

Beta-human chorionic gonadotrophin (β HCG) will be assessed in all women as specified in the schedule of assessments [Section 18.1](#).

Information regarding pregnancies occurring during the study up to 30 days after discharge of the study must be collected and reported to the sponsor as an SAE. The sponsor will request further information from the investigator as to the course and outcome of the pregnancy.

The investigator must instruct all women to inform him immediately should they become pregnant. The investigator should counsel the subject, discuss the risks of continuing with the pregnancy and the possible effects on the foetus. Monitoring of the subject should continue until conclusion of the pregnancy.

Investigators must instruct all men to inform them immediately should his sexual partner become pregnant during the study.

If the investigator becomes aware of a pregnancy occurring in the partner of a subject participating in the study, this should be reported to the sponsor. After the partner has given signed written consent, the investigator should counsel the woman, discuss the risks of continuing with the pregnancy and the possible effects on the foetus. Monitoring of the subject's partner should continue until conclusion of the pregnancy, which may involve follow-up after the subject's involvement in the study has ended.

7.1.6 Deaths

All AEs resulting in death either during the study period or within 30 days after the last dose must be reported as a SAE.

The convention for recording death is as follows:

- AE term: Lead cause of death (e.g. multiple organ failure, pneumonia, myocardial infarction),
- Outcome: Fatal.

The only exception is if the cause of death is unknown (i.e. sudden or unexplained death), in which case the AE term may be "death" or "sudden death".

7.1.7 Reporting to Competent Authorities, IECs/IRBs and other Investigators

The sponsor will ensure that processes are in place for submission of reports of SUSARs occurring during the study to the Competent Authorities (CAs), Independent Ethics Committees (IECs)/Institutional Review Boards (IRBs) and other investigators or clinicians who may be administering the study drug.

Reporting will be done in accordance with the applicable regulatory requirements.

The sponsor must report all SUSARs to European Medicines Agency's (EMA) EudraVigilance database within 15 days. Fatal and life-threatening SUSARs should be reported within seven calendar days, with another eight days for completion of the report.

The sponsor can prepare additional reports for other authorities (e.g. FDA).

7.2 Specific Safety Assessments

The investigator is responsible to monitor subjects' safety at any time during the study.

For each assessment performed, the investigator must document his review of the result(s) in the source document(s). In case of abnormal result or value(s) falling outside of predefined normal ranges, the investigator should specify whether the finding is considered as "clinically significant" (CS) or "not clinically significant" (NCS).

Any finding, whether judged CS or NCS may lead to retest at the discretion of the investigator.

7.2.1 *Physical examinations*

Physical examinations (including height, body weight and body temperature) will be conducted as presented in the schedule of assessments in [Section 18.1](#).

Any changes from baseline in physical examination findings judged to be clinically significant by the investigator will be recorded as AEs. Any physical examination findings (abnormalities) persisting at the end of the study will be followed by the investigator until resolution or until reaching a clinically stable endpoint.

7.2.2 *Vital signs*

Vital signs (VS), including systolic and diastolic blood pressure (SBP and DBP), heart rate, will be assessed as presented in the schedule of assessments in [Section 18.1](#).

Assessments of SBP, DBP and heart rate will be performed with an automated device so that measurements are independent of the observer. These parameters will be recorded after at least five minutes rest in supine position.

7.2.3 *Electrocardiograms*

Twelve-lead computerised standard ECGs, with paper printout, will be obtained while subject is in resting supine position for at least five minutes and until four regular consecutive complexes are available, at timepoints presented in the schedule of assessments in [Section 18.1](#).

For each timepoint, computerised standard ECGs will be recorded so that the following parameter can be automatically calculated and reported on the ECG paper printout:

- Sinus rhythm,
- RR interval duration or heart rate,
- PR interval duration,
- QRS interval duration,
- QT interval duration,
- QT interval corrected by the Fridericia's methodology.

Automated ECG interval data will be interpreted by a qualified physician at the site as soon after the time of ECG collection as possible, and ideally while the subject is still present, for immediate subject management. The qualified physician will document his review and interpretation (including evaluation of clinical significance in case of abnormality) on every ECG printout.

The paper printouts will be kept in the source documents at site. Only the interpretation and abnormalities will be reported in the CRF for integration with other clinical study data. These paper ECGs may be subject to further review, if appropriate.

Clinically significant changes, in the judgement of the investigator, in the abovementioned parameters will be recorded as AEs.

7.2.4 *Clinical laboratory tests*

Blood and urine samples collection will be performed for standard clinical laboratory tests, including biochemistry, haematology, coagulation and urinalysis panels, as well as specific tests such as urine drug screening, breath ethanol tests and pregnancy tests for women of childbearing potential, at timepoints indicated in the schedule of assessments in [Section 18.1](#).

Full details related to the samples processing, labelling, storage, shipment and destruction procedures will be documented in a stand-alone document (i.e. laboratory manual).

The results of laboratory tests performed during the screening phase including Day-1 must be obtained before dosing on Day 1.

The investigator will review each safety laboratory test results, document the review, and record any clinically significant changes as AEs.

All clinically significant out of normal range laboratory tests occurring during the study may be repeated at appropriate intervals until they return to baseline or to a level deemed acceptable by the investigator or until the abnormality is explained by an appropriate diagnosis that do not require further follow-up.

7.2.4.1 *Blood Analyses*

Parameters to be assessed are listed in [Section 18.3](#).

7.2.4.2 *Urinalysis*

Freshly voided urine samples (at least 10 mL) will be collected to perform a dipstick assessment of the parameters listed in [Section 18.3](#). In case of abnormal result on the dipstick, a confirmatory analysis or additional assessments might be requested to the local laboratory, at the discretion of the investigator.

Microscopy will be performed, if indicated, but results will not be collected in the CRF. If in the opinion of the investigator there are any clinically significant abnormalities in microscopy, they will be recorded as an AE in the CRF.

7.2.4.3 *Pregnancy Test*

Beta-human chorionic gonadotrophin (β HCG) will be assessed in all female subjects as specified in the schedule of assessments in section 18. It may be repeated at any time during the study according to investigator's judgement.

7.2.4.4 *Drug of Abuse / Alcohol testing*

Urine drug screen and breath alcohol testing will be performed as specified in [section 18](#) and at any time at the discretion of the investigator.

8 PHARMACOKINETIC ASSESSMENTS

Detailed procedures for the collection, processing, labelling, storage, shipment and destruction of the samples will be provided in stand-alone documents (laboratory manual, PK sample management plan).

Pharmacokinetic blood samples will be collected predose (time 0) and up to 72 hours postdose. Sampling timepoints are presented in the study schedule of assessments in [Section 18.1](#).

Urine samples will be collected predose, and up to 72 hours postdose. Collection intervals are presented in the study schedule of assessment in [Section 18.1](#).

Plasma and urine concentrations of telotristat ethyl and its active metabolite (telotristat) will be determined by validated liquid chromatography/tandem mass spectrometry (LC-MS/MS) methods.

The following PK parameters for total telotristat ethyl, its active metabolite (telotristat) and the inactive metabolite LP-951757, will be determined (where possible):

- C_{\max} Maximum plasma concentration
- AUC_{inf} Area under the concentration-time curve (AUC) from 0 to infinity
- $AUC_{0-t_{\text{last}}}$ AUC from 0 to the last quantifiable concentration
- t_{\max} Time to maximum plasma concentration
- $t_{1/2}$ Apparent terminal elimination half life
- λ_z Apparent first order terminal elimination rate constant
- CL/F Apparent total clearance from plasma
- V_z/F Apparent volume of distribution
- f_u Unbound plasma fraction

The amount of unchanged telotristat ethyl and its active metabolite (telotristat) excreted in urine (A_e) will also be determined (where possible).

The ratio active metabolite (telotristat)/telotristat ethyl and the ratio active metabolite (telotristat)/[telotristat ethyl + active metabolite (telotristat)] will also be determined for C_{\max} and AUC.

The mean fraction f_u will be used to derive the following PK parameters for unbound telotristat ethyl and its active metabolite (telotristat):

- C_{\max} Maximum plasma concentration
- AUC_{inf} Area under the concentration-time curve (AUC) from 0 to infinity
- $AUC_{0-t_{\text{last}}}$ AUC from 0 to the last quantifiable concentration
- CL/F Apparent total clearance from plasma
- V_z/F Apparent volume of distribution

Protein binding

Blood samples will be collected for protein binding of telotristat ethyl, its active metabolite (telotristat) and the inactive metabolite LP-951757 at various timepoints postdose. Sampling timepoints for protein binding assessment are presented in the study schedule of assessments in [Section 18.1](#).

Plasma protein binding will be assessed using equilibrium dialysis followed by LC-MS/MS for determination of unbound drug concentrations.

The parameter f_u unbound plasma fraction will be determined (where possible) for telotristat ethyl, its active metabolite (telotristat) and the inactive metabolite LP-951757. PK parameters may also be expressed in terms of unbound concentrations (e.g. C_{maxu} , AUC_u , CL_u/F), if applicable.

9 PHARMACODYNAMIC/EFFICACY ASSESSMENTS

Not applicable.

10 EXPLORATORY ASSESSMENTS

Not applicable.

11 STATISTICAL ANALYSES

11.1 Analyses Populations

The following populations will be used for statistical analyses:

- Screened population: All subjects screened (i.e. who signed the informed consent),
- Safety population: All subjects who received the single oral dose of study drug,
- Pharmacokinetics valid population: All subjects who received the single oral dose and have no major protocol deviations affecting the PK variables and for whom the renal function group is assessable and who have a sufficient number of plasma concentrations to estimate the main PK parameters.

11.2 Sample Size Calculation

No prospective calculations of statistical power are made. The sample size (eight subjects per group) is selected to provide information on PK following single oral dose of telotristat etiprate. Safety and tolerability will be evaluated as secondary parameters.

These number of subjects per group are mentioned in the FDA and EMA guidelines. Based on previous data from subjects treated with a single dose of 250 mg (53% coefficient of variation), eight subjects per group will provide 84% power to detect a 2-fold difference in AUC_{inf} between the renal impaired group and the control group with normal renal function.

Subjects who withdraw from the study or do not complete the study may be replaced as deemed necessary after agreement between the sponsor or its representative and investigator.

11.3 Significance Testing and Estimations

A 90% confidence interval (CI) will be calculated for the geometric least square mean ratios from analysis of variance (ANOVA) on the log transformed C_{max} , AUC_{inf} and $AUC_{0-tlast}$ to illustrate the difference between renal impaired group versus the control group with normal renal function.

Moreover, 90% CI of the median difference for t_{max} will be produced.

The statistical analysis of safety is only descriptive therefore no formal statistical significance testing will be performed.

11.4 Statistical Methods

Statistical analyses will be performed by an external contract research organisation (CRO), managed by the sponsor's biometry department.

A statistical analysis plan (SAP) will describe the planned statistical analysis in detail. Tables, figures, and listings (TFLs) templates will be developed as a separate document.

An overview of the main analysis strategy is provided in the following sections.

Any deviation from the original SAP will be described and justified in the final report.

11.4.1 Demographic Characteristics

Descriptive summary statistics (n, mean, standard deviation (SD), median, minimum, maximum) or frequency counts of demographic (age, height, weight and body mass index) will be presented overall for the safety population.

Baseline data (medical history, concomitant disease (predose AEs and ongoing medical history, prior medications and therapies, baseline symptoms, etc) will be presented by renal function group and overall for the safety population.

11.4.2 *Subject Disposition and Withdrawals*

The numbers and percentages of subjects screened and included in each of the PK and safety populations will be tabulated. The reasons for subject exclusions from PK populations will also be tabulated. Primary reasons for discontinuation of study treatment will be tabulated.

11.4.3 *Safety Evaluation*

Summaries will be presented by renal function group and, as needed, by timepoint.

All AEs will be coded according to the latest version of the Medical Dictionary for Regulatory Activities (MedDRA).

Study drug treatment-emergent AE (TEAE) summaries will include the overall incidence (by system organ class and preferred term), events by maximum intensity, events by relationship to study drug, events leading to discontinuation of study drug, and SAEs.

Physical examination findings, vital signs, ECG recordings and clinical laboratory parameters (biochemistry, haematology, coagulation and urinalysis) will be summarised descriptively at each timepoint. Actual and change from baseline data will be calculated and summarised where data are available. The investigator's interpretation of 12-lead ECGs will be listed. In addition, a listing will be presented of all values for a subject with at least a clinically significant abnormal laboratory value.

Concomitant medications will be coded by using the latest version of the World Health Organisation (WHO) drug dictionary and will be summarised by renal function group and by overall with the number and percentage of subjects receiving concomitant medication by drug class and preferred drug name.

11.4.4 *Pharmacokinetic Evaluation*

Arithmetic means, coefficients of variation (CV), standard deviation (SD), median, minimum and maximum values, and number of observations will be calculated for each renal function group. Geometric mean and geometric CV will be provided for all PK parameters except t_{max} . Median, minimum, maximum, and number of observations will be calculated for t_{max} .

An analysis of variance (ANOVA) will be performed separately for the groups with a renal impaired function, on the natural log-transformed telotristat ethyl and the active metabolite (telotristat) C_{max} , $AUC_{0-tlast}$, and AUC_{inf} . The repeated-measures ANOVA, which takes into account the fact that the measures are correlated, will be performed using a linear mixed effects model, with renal function group as a fixed term. An estimate and 90% CI for the geometric least squares mean (LSM) ratios for each renal impaired group (test) versus the control group with normal renal function (reference) will be provided for C_{max} , $AUC_{0-tlast}$, and AUC_{inf} .

Ratios of LSM will be calculated using the exponentiation of the difference between treatment LSM from the analyses on the log-transformed C_{max} , $AUC_{0-tlast}$, and AUC_{inf} . These ratios will be expressed as a percentage relative to the reference group (test [mild, moderate, or severe renal impaired groups] versus reference [control group with normal renal function]). The 90% CIs will be obtained for the difference between the LSM (test minus reference) resulting from the analyses of the log-transformed C_{max} , $AUC_{0-tlast}$, and AUC_{inf} .

The t_{max} will be analysed using nonparametric analysis (Walsh averages and appropriate quantile of the Wilcoxon signed rank test statistic). The median difference between the test and reference groups and the corresponding 90% CI for the difference will be calculated.

Protein binding

The following parameter will be determined (where possible) for telotristat ethyl, its active metabolite (telotristat) and the inactive metabolite LP-951757: f_u unbound plasma fraction.

PK parameters may also be expressed in terms of unbound concentrations (e.g. C_{maxu} , AUC_u , CL_u/F), if applicable.

11.4.5 Interim Analyses

There will be an interim analysis of PK and safety data following the completion of subjects with severely impaired renal function and demographically-matched healthy subjects with normal renal function (Part A) to determine whether subjects with mildly, and moderately impaired renal function (Part B) will be enroled in the study.

The decision to dose eight subjects with mildly impaired renal function and eight subjects with moderately impaired renal function will be based on the PK evaluation of the Part A subjects and the observation of a 2-fold increase in total and unbound fraction of either the maximal plasma concentration (C_{max}) or plasma exposure (AUC) of the active metabolite telotristat.

Decision will not be based on the PK evaluation of the telotristat ethyl since it is rapidly converted to its active metabolite, but also because its PK profile might not be fully characterised because of anticipated low (or below limit of quantification) plasma concentrations.

This 2-fold increase in total and unbound fraction of either the C_{max} or AUC of the active metabolite (telotristat) in subjects with severely impaired renal function as compared to healthy subjects with normal renal function is a clinically relevant increase and considered as a conservative approach for further PK investigations in subjects with mildly and moderately impaired renal function.

Indeed, in a previous study in healthy subjects (20), 250 mg telotristat etiprate given as a tablet led to a mean maximal plasma concentration (C_{max}) of 449 ng/mL (corresponding to 1.60 ng/mL unbound C_{max} based on an f_u of 0.356%) and a mean plasma exposure (AUC_{inf}) of 1305 h.ng/mL of the active metabolite (telotristat) (corresponding to 4.65 h.ng/mL unbound AUC based on an f_u of 0.356%) (see [Table 2](#) below).

A 2-fold increase in total and unbound fraction of either the mean C_{max} or AUC of the active metabolite (telotristat) would lead to approximately 900 ng/mL (corresponding to 6.40 ng/mL unbound C_{max} based on a 2-fold increase f_u of 0.712%) and 2600 h.ng/mL (corresponding to 18.51 h.ng/mL unbound AUC based on a 2-fold increase f_u of 0.712%) respectively. This mean plasma concentration is close to the one reported following a single oral dose of 1500 mg of telotristat etiprate (given to healthy subjects as six 250-mg tablets) from a previous study (21), while the exposure is below:

- Mean C_{max} of 1818 ng/mL (corresponding to 6.47 ng/mL unbound C_{max}),
- Mean AUC_{inf} of 12634 h.ng/mL (corresponding to 44.98 h.ng/mL unbound AUC).

In this study, 1500 mg single dose level was safe and well tolerated by the subjects.

**Table 2 Pharmacokinetic parameters of the active metabolite (telotristat)
following single dose of 250 mg telotristat ethyl**

Parameter	Treatment A: 250 mg LX1606-Capsule				Treatment B: 250 mg LX1606-Tablet			
	n	Mean	SD	CV%	n	Mean	SD	CV%
T _{max} (hr)	22	3.73	0.94	25.09	22	1.23	0.69	55.84
C _{max} (ng/mL)	22	340	152	44.53	22	449	251	55.92
AUC _{last} (hr*ng/mL)	22	1297	525.9	40.55	22	1285	692.2	53.87
AUC _{inf} (hr*ng/mL)	21	1355	501.1	36.97	22	1305	699.7	53.62
AUC _{Extrap} (%)	21	2.60	6.42	246.58	22	1.67	0.55	32.98
λ _z (hr ⁻¹)	21	0.2253	0.0816	36.20	22	0.2140	0.0980	45.81
T _{1/2} (hr)	21	3.59	2.06	57.44	22	3.90	1.57	40.13
T _{last} (hr)	22	22.09	5.03	22.78	22	20.18	5.72	28.35
C _{last} (ng/mL)	22	5.82	9.18	157.66	22	3.67	1.26	34.40

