	
equal or above 90 mL/min). The PK and protein binding analysis of telotristat ethyl, its active metabolite (telotristat) and the inactive metabolite LP-951757 will be assessed in eight subjects with severely decreased renal function and compared to those in eight demographically-matched subjects with normal renal function (GFR \geq 90 mL/min) following single oral dose of 250 mg telotristat ethyl. If results of Part A show a substantial effect (set as 2-fold increase in total and unbound of either the maximal plasma concentration (C_{max}) or plasma exposure (AUC) of the active metabolite (telotristat)), the PK and protein binding analysis of telotristat ethyl, its active metabolite (telotristat) and the inactive metabolite LP-951757 will also be assessed in eight subjects with a mildly (GFR between 60 and 89 mL/min, both inclusive) and eight subjects with a moderately (GFR between 30 and 59 mL/min, both inclusive) decreased renal function (Part B) following single oral dose of 250 mg telotristat ethyl. Safety and tolerability of the single oral dose of 250 mg telotristat ethyl will also be evaluated.
 
Renal function will be classified based on estimated GFR as determined by the Modification of Diet in Renal Disease (MDRD) formula.
 
After a maximum 28-day screening period (56 days for subjects with mildly and moderately impaired renal function), eligible subjects will begin their stay at the clinical unit on Day-1 (admission day). Subjects will receive a single oral dose of telotristat etiprate (as one tablet containing 250 mg telotristat ethyl) on Day 1. Following safety assessments, subjects will be discharged from the clinical unit either on Day 2 or Day 4. In the first option (discharge on Day 2), subjects will return to the clinical unit for outpatient visits on Day 3 and Day 4 for PK blood sampling and supply of urine collected at home. In the second option (involving a stay up to Day 4), subjects will have safety assessments performed on Day 2 and will be discharged upon completion of PK blood samplings and urine collection on Day 4. All subjects will return to the clinical unit for an end of study (EOS) visit no less than seven days after dose administration (between Day 8 and Day 15).

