3 INVESTIGATIONAL PLAN

3.1 Overall Study Design and Plan

This will be an open-label single dose staged study starting with a Part A. Part A will include two groups, a test group and a control group. The test group will include eight subjects with a GFR as low as possible (i.e. < 20 mL/min), but not requiring dialysis. If inclusion of such subjects is not possible, subjects with severely decreased renal function (i.e. with a GFR between 15 and 29 mL/min, both inclusive) may be included. The test group will be compared to a control group of eight demographically-matched healthy subjects with normal renal function (i.e. with a GFR equal or above 90 mL/min) (Table 1).

The PK and protein binding of telotristat ethyl and its active metabolite (telotristat) following administration of a single oral dose of 250 mg telotristat ethyl will be evaluated. If the results from Part A of the study show a substantial effect (set as 2-fold increase in either the maximal plasma concentration (C_{max}) or plasma exposure (AUC) of the active metabolite (telotristat), PK and protein binding analysis of telotristat ethyl and its active metabolite (telotristat) will also be assessed in Part B in eight subjects with a mildly and eight with a moderately decreased renal function (see Table 1 for renal function groups definition) following administration of a single oral dose of 250 mg telotristat ethyl. Safety and tolerability of the single oral dose of 250 mg telotristat ethyl will also be evaluated.

After a maximum 28-day screening period (56 days for subjects with mildly and moderately impaired renal function), eligible subjects will begin their stay at the clinical unit on Day-1 (admission day). Subjects will receive a single oral dose of telotristat etiprate (as one tablet containing 250 mg telotristat ethyl) on Day 1. Following safety assessments, subjects will be discharged from the clinical unit either on Day 2 or Day 4. In the first option (discharge on Day 2), subjects will return to the clinical unit for outpatient visits on Day 3 and Day 4 for PK blood sampling and supply of urine collected at home. In the second option (involving a stay up to Day 4), subjects will have safety assessments performed on Day 2 and will be discharged upon completion of PK blood samplings and urine collection on Day 4. All subjects will return to the clinical unit for an end of study (EOS) visit no less than seven days after dose administration (between Day 8 and Day 15).

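### The Part B trigger is worded three ways, and the protocol's worked example of the 2-fold rule is a 4-fold rise in unbound telotristat

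*Protocol*

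**What the plan says.** The criterion for opening Part B is stated in five places in current text:

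- **Protocol 3.1:** "set as 2-fold increase in either the maximal plasma concentration" or AUC of telotristat. No unbound condition appears.
- **Protocol Synopsis, and SAP 1.2 in the same words:** "set as 2-fold increase in total and unbound of either the maximal plasma concentration" or AUC.
- **Protocol 11.4.5, and SAP 3.2.17 in the same words:** "the observation of a 2-fold increase in total and unbound fraction of either the maximal plasma concentration" or AUC.

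Protocol 11.4.5 then illustrates the rule. It takes mean telotristat Cmax 449 ng/mL and AUCinf 1305 h.ng/mL from an earlier healthy-subject study. With fu 0.356%, it gives unbound values of 1.60 ng/mL and 4.65 h.ng/mL. At the trigger it gives totals of about 900 and 2600, and unbound values of 6.40 and 18.51 "based on a 2-fold increase f_u of 0.712"%.

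The section adds: "This mean plasma concentration is close to the one reported following a single oral dose of 1500 mg of telotristat etiprate", while the AUC is lower. For 1500 mg it reports Cmax 1818 ng/mL ("corresponding to 6.47 ng/mL unbound") and AUCinf 12634 h.ng/mL (44.98 unbound), and says that the "1500 mg single dose level was safe and well tolerated by the subjects". It says of the 2-fold criterion that it "is a clinically relevant increase and considered as a conservative approach".

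**The concern.** A go/no-go rule should give one answer for one set of data. Here, one statement ignores binding, one requires a doubling of unbound exposure as well as total, and one can be read as requiring fu itself to double. The last two differ materially, because unbound exposure is the product of total and fu.

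The wording of 11.4.5 alone does not settle what unbound fraction means. SAP 3.1.7 uses the term loosely for unbound PK parameters. Protocol 1.4, SAP 3.1.4 and SAP 3.2.2.4.3 use it for fu, and the 11.4.5 example doubles fu explicitly.

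Two things are at stake:

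- whether 16 subjects with mild and moderate impairment are dosed;
- whether the 1500 mg comparison, which is the support offered for the threshold, describes the rule that will be applied.

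If the wording stays open until Part A is read, the threshold could in effect be chosen with the results in view.

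**Working it through.** **Formula.** SAP 3.1.4 sets unbound Cmax = Cmax × Fu and unbound AUC = AUC × Fu. Let R be the severe-to-healthy ratio of total exposure and F the ratio of fu. The unbound ratio is then R × F. This is exact for an individual and for geometric means. It is approximate if fu is compared on arithmetic means, and SAP 3.2.2.4.3 does analyse fu untransformed.

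**Step 1: reproduce the plan's figures.**

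- Baseline: 449 × 0.00356 = 1.60; 1305 × 0.00356 = 4.65.
- Trigger example: 900 × 0.00712 = 6.41 (stated as 6.40; 2 × 449 = 898 gives 6.39); 2600 × 0.00712 = 18.51.
- 1500 mg: 1818 × 0.00356 = 6.47; 12634 × 0.00356 = 44.98.

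All agree to rounding. The multiplication is sound; the question is what rule it illustrates.

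**Step 2: fold-rises in the example.**

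- Total: 900/449 = 2.00; 2600/1305 = 1.99.
- fu: 0.712/0.356 = 2.00.
- Unbound: 6.40/1.60 = 4.00; 18.51/4.65 = 3.98.

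**Step 3: values for a 2-fold unbound rise.** With total doubled and fu unchanged, unbound Cmax is 900 × 0.00356 = 3.20 ng/mL. Unbound AUC is 2 × 1305 × 0.00356 = 9.29 h.ng/mL (9.26 from the rounded 2600).

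**Step 4: comparison with 1500 mg.**

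| Quantity | At trigger | 1500 mg | Ratio |
|---|---|---|---|
| Unbound Cmax, as written | 6.40 | 6.47 | 99% |
| Unbound Cmax, 2-fold | 3.20 | 6.47 | 49% |
| Total Cmax | 900 | 1818 | 49.5% |
| Unbound AUC, as written | 18.51 | 44.98 | 41% |
| Unbound AUC, 2-fold | 9.29 | 44.98 | 21% |
| Total AUC | 2600 | 12634 | 20.6% |

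The word *close* fits the first row only.

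**Step 5: do the statements give different decisions?** Protocol 3.1 needs R ≥ 2. The Synopsis and SAP 1.2 need R ≥ 2 and R × F ≥ 2. Protocol 11.4.5 and SAP 3.2.17, read as fu, need R ≥ 2 and F ≥ 2, hence R × F ≥ 4. The R and F values below are illustrations, not figures from the documents.

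| R | F | R × F | Protocol 3.1 | Synopsis, SAP 1.2 | 11.4.5, SAP 3.2.17 read as fu |
|---|---|---|---|---|---|
| 2 | 2 | 4 | met | met | met |
| 3 | 1 | 3 | met | met | not met |
| 2 | 1.5 | 3 | met | met | not met |
| 2.2 | 0.8 | 1.76 | met | not met | not met |

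**Step 6: width of the disagreement.** The Synopsis rule needs F ≥ 2/R and the fu reading needs F ≥ 2. From a baseline fu of 0.356%, they disagree over these ranges:

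- R = 2: fu from 0.356% to just under 0.712%.
- R = 3: fu from 0.356% × 2/3 = 0.237% to just under 0.712%.

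Protocol 3.1 and the Synopsis disagree at R = 2.2 when fu is below 0.356% × 2/2.2 = 0.324%.

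**Step 7: the fu reading at large R.** With fu unchanged, unbound Cmax reaches the 1500 mg value at R = 6.47/1.60 = 4.04. On the fu reading, Part B would still not be triggered.

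**The case against.** The best defence is that there are really two wordings. The unbound fraction of Cmax or AUC can be read as the unbound part of those parameters, since fu is not a property of either. On that reading four of the five statements agree, Protocol 3.1 is an abbreviated summary, and the example simply doubles one factor too many. The example also states its premise about fu openly, and its arithmetic follows from that premise. On every reading, the example's values stay below the 1500 mg values, and if a 2-fold unbound rise is meant, the true margin is larger than the text implies.

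The practical reach is limited too. The statements diverge only if total telotristat at least doubles. Less than 1% of the dose was recovered in urine (Protocol 1.4). A committee takes the decision, its charter is not available here and may already fix the rule, and Part A is reported in any case.

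These points limit the impact but do not repair the text. If unbound Cmax or AUC is meant, the two worked values and the 1500 mg comparison are wrong. If fu is meant, the Synopsis and SAP 1.2 state a different rule. Protocol 3.1 is out of line on either reading. Low urinary recovery does not rule out divergence: Protocol 1.4 draws no conclusion for severe impairment (n = 5), and the effect on binding is a study objective. Protocol 3.1.1 describes the charter as covering the data reviewed and attendees; nothing shows that it settles the criterion.

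**Conclusion.** The concern holds. The Part B criterion is inconsistent across the Protocol and SAP, and the 11.4.5 illustration of a 2-fold rule is a 4-fold rise in unbound exposure (4.00 for Cmax, 3.98 for AUC). The claimed closeness to 1500 mg depends on that 4-fold figure.

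Which part is wrong depends on intent. If unbound exposure is meant, the example overstates the trigger level by a factor of about two. If fu is meant, Part B needs at least a 4-fold unbound rise, and a large rise in total with unchanged binding would never trigger it; describing that rule as 2-fold and conservative would need its own support.

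The conclusion rests on the SAP's definition of unbound exposure as total times Fu and on the protocol's own figures. How likely Part A is to fall where the statements disagree cannot be judged from the documents. Because this is the stated criterion for dosing a further 16 subjects, it must be corrected before Part A is read.

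**What to change.** - Reconcile the Protocol Synopsis, 3.1 and 11.4.5, SAP 1.2 and 3.2.17, and the committee charter to one rule. State whether an unbound condition applies and, if so, whether it refers to unbound Cmax and AUC or to fu. The choice is the sponsor's.
- Recompute the two unbound trigger values and the 1500 mg comparison in 11.4.5 under that rule, and revise the claims of closeness and conservatism to match.
- In the same edit, name the estimate compared with 2, for example the planned geometric LSM ratio, unless the charter already does so.

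The cost is wording in five places and the charter, plus a short recalculation. Sample size, visits and assays do not change.
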